## 1. Background

The prevalence of overweight and obesity worldwide increases significantly with concomitant diseases. Disruption of energy balance is known as the main cause of obesity. To maintain energy balance, weight control (dietary intervention, physical activity, behavioral therapy) results in short-term weight loss, but sustained weight maintenance is difficult. So alternative weight-loss strategies can be a solution (1). Epidemiological studies show that high dietary fiber intake is associated with lower body weight and waist circumference (2,3). The controlled intervention studies report that weight gain can be prevented by reducing appetite and energy intake with high dietary fiber intake (4–7). In addition, most studies show that high fiber intake is also associated with improved postprandial glycemic response (8). These potential beneficial effects of dietary fiber, which is divided into two as soluble and insoluble according to its physiological effects, can be attributed to  $\beta$ -glucan, a type of soluble fiber (9). However, results from studies examining the effects of  $\beta$ -glucan on appetite are not consistent and the underlying mechanisms are not yet clear. It is thought to contribute to a feeling of satiety by increasing the duration of oral exposure to food and abdominal distension and by increasing short-chain fatty acid production as a result of colonic fermentation (10–12). The hypothesis that  $\beta$ -glucan affects appetite by acting on gastrointestinal hormones is still controversial (13). On the other hand, the blood-glucose-lowering properties of  $\beta$ -glucan derived from oats and barley have been confirmed by the European Food Safety Authority (EFSA), with a health claim that 4 g  $\beta$ -glucan can be used per 30 g of available carbohydrates per meal (14). The lowering effects of  $\beta$ -glucan on blood glucose and insulin levels and blood pressure are speculated to be due to its prebiotic properties and its effects on weight loss (9).

Overall, although studies have shown positive effects of  $\beta$ -glucan on appetite and postprandial glycemic response, it is not yet clear whether this positive effect is due to  $\beta$ -glucan or total dietary fiber intake. Also, since the majority of studies used products enriched with  $\beta$ -glucan, little is known about the possible effects of dietary sources with  $\beta$ -glucan in their natural form. In this study, the effects of breads derived from barley and oat, which are the best grain sources of  $\beta$ -glucan, on appetite and postprandial glycemia were examined and the possible effects of its natural dietary sources were determined. In addition, the effects of breads, which are a source of  $\beta$ -glucan, on appetite and postprandial glycemia were evaluated by comparing not only with white bread (WB) but also with whole wheat bread (WWB), unlike previous studies. In this way, it was aimed to determine whether the possible positive effects were due to  $\beta$ -glucan or total dietary fiber intake. The selection of bread, which is the most commonly consumed grain-based food in European countries, as the test food will make it easier to add possible positive results to healthy eating recommendations and to their applicability.

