## 2. Objective

This study aimed to compare the postprandial effects of  $\beta$ -glucan on glycemia and appetite of breads derived from oats and barley, which are the best natural grain sources. In addition, the positive health effects of  $\beta$ -glucan were sought to be determined independent of total dietary fiber intake, using not only WB as the control food but also WWB, which has a dietary fiber content equal to that of breads containing  $\beta$ -glucan.

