### 3.2. Chemical Analysis

In this research, total fat, protein,  $\beta$ -glucan, total available carbohydrate, and total dietary fiber analyzes were performed chemically in the flour and bread samples. Chemical analyzes were performed in parallel and in duplicate. Data were reported on dry matter and average values of at least two analyzes were taken. The energy value (kcal) per test portion was calculated using the weight (g) of each test portion and the formula  $[(4 \times \text{protein}) + (9 \times \text{fat}) + (4 \times \text{available carbohydrate})]$  (19). All chemical analyzes were conducted in Erciyes University Veterinary Faculty Food Hygiene and Technology Laboratory.

All chemical analysis was performed as described above by taking a sample of several flours commonly available in Turkey. Among these flours, barley and oat flours with the highest  $\beta$ -glucan content were selected for baking bread as well as white flour and whole wheat flour having the most similar macronutrient content with barley and oat flours. A preliminary study was conducted to evaluate  $\beta$ -glucan content and bread baking tests were applied. For BB and OB, the content of  $\beta$ -glucan was targeted to be about 3 g in one serving. WB and WWB were used as reference and control foods, respectively. After the test breads were prepared, all the chemical analyzes described above were carried out again and the nutritional composition of the breads was found as in Table 1.

**Table 1.** Energy and macronutrient contents of test breads

	White bread	Whole-wheat bread	Barley bread	Oat bread
Portion size (g)	72	73	73	70
Energy (kcal)	150	147	154	133
Carbohydrate (g)	28.7	27.3	28.9	23.9
Protein (g)	5.0	5.7	4.9	4.7
Fat (g)	1.7	1.7	2.1	2.0
Dietary fiber (g)	2.2	6.8	6.9	9.0
$\beta$ -glucan (g)	1.2	1.4	3.1	3.2

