### 3.3. Baking The Test Breads

For WB, WWB, BB, and OB, baking tests were performed using 100% white flour, whole wheat flour, barley flour, and oat flour, respectively. All breads have similar ingredients except the types of flour used. Dry yeast (2 g / 100 g), sugar (4 g / 100 g), salt (2 g / 100 g), and sunflower oil (4 g) in all breads were added (based on 100 g flour) (20). After resting for 30 minutes at room temperature (25 °C), the samples were fired in an electric oven at 180 °C for

30 minutes (21)(20). One serving size slices were wrapped in aluminum foil and packed in plastic bags to prevent drying and stored at -18 °C until use (22).

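### β-glucan is aliased with flour in all four breads, so the plan can compare the breads but cannot attribute a difference to β-glucan as Sections 1 and 2 intend

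*Combined protocol and SAP*

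**What the plan says.** The Background (Section 1) notes that earlier work leaves open whether benefits come from β-glucan or from total fibre, and offers the comparison with both white bread (WB) and whole-wheat bread (WWB) as the answer: "In this way, it was aimed to determine whether the possible positive effects were due to" the one or the other.

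Section 2 has two parts. The first is to compare the postprandial effects of β-glucan "on glycemia and appetite of breads derived from oats and barley, which are the best natural grain sources". The second is to find effects of β-glucan independent of total fibre, with WWB as a control "which has a dietary fiber content equal to that of breads containing" β-glucan.

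Section 3.3 describes the breads: "baking tests were performed using 100% white flour, whole wheat flour, barley flour, and oat flour, respectively". The other ingredients are similar. Section 3.2 sets a target of about 3 g β-glucan per serving for both barley bread (BB) and oat bread (OB). Table 1 gives the composition in the order WB, WWB, BB, OB: "glucan (g) 1.2 1.4 3.1 3.2", "Dietary fiber (g) 2.2 6.8 6.9 9.0" and "Carbohydrate (g) 28.7 27.3 28.9 23.9".

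Section 4.2 plans a one-way repeated-measures ANOVA across breads. It has no composition term and no statement of how a difference between breads is to be interpreted.

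**The concern.** The aim is causal attribution to one component, but the factor that is randomised is the bread. Replacing the whole flour changes β-glucan, total fibre, carbohydrate and every unmeasured property of the grain together. Ruling out total fibre would therefore not leave β-glucan as the only remaining explanation.

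The first objective has a further difficulty. If two breads contain the same amount of β-glucan, a difference between them says nothing about the amount of β-glucan; it reflects whatever else differs.

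The stake is the conclusion rather than the data. The Background expects positive results to feed into healthy-eating recommendations. Advice naming β-glucan is a different claim from advice naming barley bread, and only the second kind can rest on this design.

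**Working it through.** **Inputs.** All are per portion, from Table 1 in Section 3.2.

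| | WB | WWB | BB | OB |
|---|---|---|---|---|
| β-glucan (g) | 1.2 | 1.4 | 3.1 | 3.2 |
| Dietary fibre (g) | 2.2 | 6.8 | 6.9 | 9.0 |
| Carbohydrate (g) | 28.7 | 27.3 | 28.9 | 23.9 |
| Protein (g) | 5.0 | 5.7 | 4.9 | 4.7 |
| Fat (g) | 1.7 | 1.7 | 2.1 | 2.0 |
| Stated energy (kcal) | 150 | 147 | 154 | 133 |

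**Step 1: is the table consistent?** Energy = 4 × protein + 9 × fat + 4 × carbohydrate (Section 3.2).
- WB: 20.0 + 15.3 + 114.8 = 150.1
- WWB: 22.8 + 15.3 + 109.2 = 147.3
- BB: 19.6 + 18.9 + 115.6 = 154.1
- OB: 18.8 + 18.0 + 95.6 = 132.4

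All four agree with the stated values within 1 kcal, so oat's low carbohydrate figure is not a misprint relative to its energy.

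**Step 2: what changes in each contrast?**

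| Contrast | β-glucan (g) | Fibre (g) | Carbohydrate (g) |
|---|---|---|---|
| OB − BB | +0.1 (+3%) | +2.1 (+30%) | −5.0 (−17%) |
| BB − WWB | +1.7 (+121%) | +0.1 (+1.5%) | +1.6 (+6%) |
| OB − WWB | +1.8 (+129%) | +2.2 (+32%) | −3.4 (−12.5%) |
| WWB − WB | +0.2 (+17%) | +4.6 (+209%) | −1.4 (−5%) |

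The common breakfast in Table 2 adds 0.66 + 0.48 + 0.30 + 16.6 = 18.04 g carbohydrate to every meal. This dilutes the oat gap but does not remove it: −5.0 / 46.94 = −10.7% against barley, and −3.4 / 45.34 = −7.5% against whole-wheat.

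**Step 3: can β-glucan be separated from flour?** Let b, f and c be the effects per gram of β-glucan, fibre and carbohydrate, and let g be everything else that changes with the flour. The expected differences are:
- BB − WWB = 1.7b + 0.1f + 1.6c + g₁
- OB − BB = 0.1b + 2.1f − 5.0c + g₂
- OB − WWB = 1.8b + 2.2f − 3.4c + (g₁ + g₂)

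The third line is the sum of the first two and adds no information. In each line any value of b can be offset by g, so b is not identified. In design-matrix terms, four flour indicators have rank 4, and adding a β-glucan column leaves the rank at 4. Dropping flour in favour of an intercept plus β-glucan, fibre and carbohydrate also gives rank 4 from four breads. That model is saturated, with nothing left to check whether flour matters. The obstacle is the set of breads, so neither more participants nor a different model would remove it.

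The one pair that shares a grain, WB and WWB, does not help: β-glucan differs by 0.2 g and fibre by 4.6 g.

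**Step 4: what each contrast supports.**
- BB versus WWB: fibre is matched, so a difference argues against total fibre amount as the cause. It does not distinguish β-glucan from other properties of barley.
- OB versus WWB: fibre and carbohydrate both differ, so even the narrower question of β-glucan or fibre is not answered.
- OB versus BB: two grain sources at about equal β-glucan. A difference cannot be assigned to the amount of β-glucan.

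**The case against.** The strongest reply is that Section 2 is loosely worded rather than wrong in substance. Read with the Background's interest in natural sources and the common 3 g target in Section 3.2, the first objective can mean a comparison of two sources at a matched β-glucan dose. Near-equality is then a strength. This stands: the fault is in describing the difference as an effect of β-glucan, not in including the contrast. The Background's choice between β-glucan and fibre also concerns WB and WWB, not oat versus barley.

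The plan does try to limit other explanations. Section 3.1 says the breads are similar in energy and macronutrients, Section 3.2 picks wheat flours close to barley and oat in macronutrients, and Section 3.3 keeps the other ingredients similar. This narrows the alternatives but leaves the grain itself, and Table 1 shows that the matching did not succeed for oat. Some confounding with grain is also the price of the deliberate choice to study β-glucan in its natural form.

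Several stronger readings are tempting, and the documents do not support them:
- That BB versus WWB is flawed because fibre other than β-glucan falls from 6.8 − 1.4 = 5.4 g to 6.9 − 3.1 = 3.8 g. At fixed total fibre, more β-glucan must mean less of the rest. If both kinds acted equally per gram, a near-null result would be the correct answer to the question about total fibre.
- That agreement of barley and oat against WWB would establish β-glucan. Both contrasts carry the same aliasing with non-wheat grain, and oat also differs from WWB in fibre and carbohydrate. Conversely, a real β-glucan effect could be hidden in an oat–barley difference caused by 5.0 g less carbohydrate.
- That the plan commits to reporting a barley advantage as a β-glucan effect. Section 4.2 contains no attribution rule. The risk comes from the stated aims combined with that silence.

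**Conclusion.** The concern holds as a limit on interpretation. The design identifies differences between four breads. It does not identify an effect of β-glucan, because each bread is a different flour and no flour appears at two β-glucan levels. One contrast of the three among WWB, BB and OB is matched on fibre: BB versus WWB, at +0.1 g fibre and +1.7 g β-glucan. Its most favourable result would be a difference that total fibre amount does not explain and that is consistent with a β-glucan effect without proving one. The equal-fibre statement in Section 2 holds for barley and fails for oat by 2.2 g (32%).

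This rests on Table 1 being accurate for the portions served. Table 1 gives no assay error, so the 0.1 g differences are best read as no difference. The aliasing itself depends on Section 3.3 alone and not on the exact figures.

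A reader might infer that the trial is invalid or that oat versus barley should be dropped. Neither follows: the comparison of the four breads as foods stands in full.

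**What to change.** In Section 2, state the objectives as effects of barley, oat, whole-wheat and white breads on glycaemia and appetite. Describe oat versus barley as a comparison of two grain sources at about equal β-glucan (3.2 vs 3.1 g). Confine the equal-fibre statement to barley versus whole-wheat, and align the closing aim in the Background.

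In Section 4.2, add three statements:
- Barley versus whole-wheat is the only fibre-matched contrast.
- A difference there will be reported as not explained by total fibre amount, and as consistent with, but not proof of, an effect of β-glucan. Other properties of the grain remain an unresolved explanation.
- Contrasts involving oat bread will not be interpreted as independent of fibre or carbohydrate.

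This needs no new data, breads or participants, and no change to the ANOVA. The cost is scientific: the trial can no longer claim an effect specific to β-glucan.

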## 2. Objective

This study aimed to compare the postprandial effects of  $\beta$ -glucan on glycemia and appetite of breads derived from oats and barley, which are the best natural grain sources. In addition, the positive health effects of  $\beta$ -glucan were sought to be determined independent of total dietary fiber intake, using not only WB as the control food but also WWB, which has a dietary fiber content equal to that of breads containing  $\beta$ -glucan.

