Since individuals were asked to fast for at least 12 hours before consuming the test meals and the postprandial response was more pronounced in the morning, breakfast was chosen as the test meal. On the day before each test meal, the participants were asked to consume their standard dinner at 20:00 and not consume any food or beverage (except water) after dinner, and not to do any physical activity other than their daily routine activities. In addition, test meals were consumed in the follicular phase of the menstrual cycle in order to control the possible effects of the menstrual cycle on appetite for female participants. Similar to previous studies (16,17), days 3-10 after the onset of menses were accepted as the follicular phase.

Participants were served barley bread (BB), oat bread (OB), and wheat breads (WB and WWB) with a standard breakfast on four different days at least two days apart (18). Breads were prepared with similar amounts of energy, protein, fat, carbohydrate, and fiber (except WB). The test meal was served to the participants at 09:00 and they were asked to consume it within 15 minutes. During the test period, participants were not allowed to eat or drink anything other

than water. On the first day of testing, participants were able to consume as much water as they wanted and the amount consumed was recorded. On the other test days, they were asked to consume the amount of water recorded on the first test day. In addition, the participants were allowed to watch movies, read books, play games on electronic devices (computer, cell phone, etc.), and do other sedentary activities during the test days, but they were not allowed to sleep.

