### 3.4. Test meals

The foods and nutritional composition of the test breakfast meals are as in Table 2.

**Table 2.** Nutritional composition of the component foods in test meals

Foods	Portion size (g)	Energy (kcal)	Carbohydrate (g)	Protein (g)	Fat (g)
Feta cheese	15	34.8	0.66	1.8	2.7
Cheddar cheese	24	79.2	0.48	5.28	6.24
Olive	24	57.1	0.30	0.32	4.79
Honey	20	64	16.6	0.06	-
Black tea	150 ml	-	-	-	-

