### 4.2. Data analysis

Statistical analysis was performed using the SPSS Statistics (version 22.0) software. Data were expressed as the mean  $\pm$  SD unless otherwise indicated. Normality was assessed using the histogram and normal Q-Q plots, and also Shapiro-Wilk test. Postprandial appetite and glucose responses were quantified as incremental area under the curve (iAUC) calculated according to the trapezoidal rule. One-way analysis of variance (ANOVA) for repeated measures was applied to determine statistical differences between groups. For all statistical analyses, p values less than 0.05 were considered to have statistical significance.

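### Oat bread does not match the whole wheat control on fibre or available carbohydrate, so a lower oat glucose response cannot be credited to β-glucan independent of total fibre

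*Combined protocol and SAP*

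**What the plan says.** Section 1 (Background) sets the question: "it was aimed to determine whether the possible positive effects were due to" β-glucan or to total dietary fibre. Section 2 (Objective) repeats it, saying that the effects of β-glucan "were sought to be determined independent of total dietary fiber intake". The means is the choice of control, "WWB, which has a dietary fiber content equal to that of breads containing" β-glucan.

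Section 3.1 makes a wider claim: "Breads were prepared with similar amounts of energy, protein, fat, carbohydrate, and fiber (except WB"). White bread (WB) is the only exception.

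The measured compositions are in section 3.2, Table 1 ("Energy and macronutrient contents of test breads"), and section 3.4, Table 2 ("Nutritional composition of the component foods in test meals"). The planned analysis in section 4.2 is: "One-way analysis of variance (ANOVA) for repeated measures was applied to determine statistical differences between groups". No handling of compositional differences is described.

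**The concern.** The inference about β-glucan needs a control bread that differs from the test bread in β-glucan and in little else that affects the outcome. Table 1 shows that whole wheat bread (WWB) does this on total fibre for barley bread (BB) but not for oat bread (OB). OB has more total fibre and less available carbohydrate than WWB, and both would be expected to lower the glucose response.

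Randomising the order of the breads does not help, because composition is fixed within each bread. The bread effect and the composition effect are the same contrast. A lower glucose iAUC after OB than after WWB could therefore be reported as a fibre-independent β-glucan effect when part or all of it came from a meal with less carbohydrate. OB versus BB has the same difficulty: β-glucan is nearly equal (3.2 v 3.1 g), but carbohydrate and fibre are not.

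**Working it through.** **Inputs.** Table 1, per portion:

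| | WB | WWB | BB | OB |
|---|---|---|---|---|
| Energy (kcal) | 150 | 147 | 154 | 133 |
| Carbohydrate (g) | 28.7 | 27.3 | 28.9 | 23.9 |
| Protein (g) | 5.0 | 5.7 | 4.9 | 4.7 |
| Fat (g) | 1.7 | 1.7 | 2.1 | 2.0 |
| Dietary fibre (g) | 2.2 | 6.8 | 6.9 | 9.0 |
| β-glucan (g) | 1.2 | 1.4 | 3.1 | 3.2 |

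Table 2, shared foods: carbohydrate 0.66 + 0.48 + 0.30 + 16.6 = 18.04 g; protein 1.8 + 5.28 + 0.32 + 0.06 = 7.46 g; fat 2.7 + 6.24 + 4.79 = 13.73 g; energy 34.8 + 79.2 + 57.1 + 64 = 235.1 kcal.

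**Step 1. Which carbohydrate is tabulated?** The formula in section 3.2 is 4 × protein + 9 × fat + 4 × available carbohydrate. Applied to Table 1 it gives 150.1, 147.3, 154.1 and 132.4 kcal, against the stated 150, 147, 154 and 133. Rounding of the inputs (up to 0.05 × 17 = 0.85 kcal) covers the oat difference. Subtracting fibre from carbohydrate first gives 141.3, 120.1, 126.5 and 96.4 kcal, which does not fit. The row is available carbohydrate, so the low oat value is a real deficit in digestible carbohydrate.

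**Step 2. Fibre against WWB.**
- BB: 6.9 / 6.8 = 1.015 (+1.5%).
- OB: 9.0 / 6.8 = 1.324 (+32%, or +2.2 g). With rounding, 8.95 / 6.85 to 9.05 / 6.75 gives +31% to +34%.

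**Step 3. Available carbohydrate.** For the bread alone, OB v WWB is 23.9 / 27.3 = 0.875 (-12.5%). Meal totals (Table 1 + 18.04 g) are WB 46.74, WWB 45.34, BB 46.94 and OB 41.94 g.
- OB v WWB: 41.94 / 45.34 = 0.925 (-3.4 g, -7.5%; -7.3% to -7.7% with rounding of Table 1).
- OB v BB: 41.94 / 46.94 = 0.893 (-5.0 g, -10.7%).
- BB v WWB: 46.94 / 45.34 = 1.035 (+1.6 g, +3.5%).

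**Step 4. Energy, OB v WWB.** Bread: 133 / 147 = 0.905 (-9.5%). Meal: 368.1 / 382.1 = 0.963 (-3.7%).

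**Step 5. What this could do to glucose iAUC.** Assume, for illustration, that iAUC is proportional to (meal carbohydrate)^e with e between 0.5 and 1. The documents do not supply e. With no β-glucan effect at all:
- OB v WWB: 0.925^0.5 = 0.962 to 0.925, i.e. -3.8% to -7.5%.
- OB v BB: 0.893^0.5 = 0.945 to 0.893, i.e. -5.5% to -10.7%.
- BB v WWB: 1.035^0.5 = 1.017 to 1.035, i.e. +1.7% to +3.5%, which works against a false benefit.

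For scale, section 4.1 sizes the trial for a 5% difference in primary outcomes, though it does not name them. No probability of a significant result can be given, because the plan states no SD for glucose iAUC.

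**Step 6. Fibre other than β-glucan.** Section 1 calls β-glucan "a type of soluble fiber". If the total-fibre assay includes it (an assumption; the assay is not described), other fibre is total minus β-glucan: WB 1.0, WWB 5.4, BB 3.8, OB 5.8 g. Of the 2.2 g oat excess over WWB, 3.2 − 1.4 = 1.8 g is then β-glucan itself.

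**The case against.** The strongest reply concerns fibre. If β-glucan is counted within total fibre, OB and WWB are close on the remainder (5.8 v 5.4 g) and BB is the bread that differs (3.8 v 5.4 g). On that reading OB has the better fibre match, and BB versus WWB compares β-glucan replacing 1.6 g of other fibre. This stands as a limit: the fibre part of the oat confounding may be small, and neither contrast isolates β-glucan perfectly. But the Objective speaks of total fibre, on which only BB is matched, and the carbohydrate gap is unaffected.

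Other points carry less weight:
- *Similar* in section 3.1 has no tolerance, the differences are openly tabulated, and the whole-meal energy gap is only -3.7%. True, but *equal* in section 2 needs no tolerance, and oat is not excepted anywhere.
- The Objective does not clearly specify an oat-versus-barley test. Fair; that contrast is secondary here.
- The ANOVA could not have adjusted for composition, since composition is constant within each bread. Correct. The remedy lies in what is concluded, not in the model.
- Table 2 does not say that its carbohydrate is available carbohydrate. Its olive row gives 4 × 0.32 + 9 × 4.79 + 4 × 0.30 = 45.6 kcal against 57.1 stated. Even if that whole gap were carbohydrate (11.5 / 4 = 2.9 g), OB v WWB would move only to about -7.1%.
- The rounding range excludes assay error, and the elasticity is assumed. Both are so; the contradiction with Table 1 depends on neither.

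**Conclusion.** The concern holds and should be fixed. The statement of equal fibre is right for barley bread and wrong for oat bread, and the statement of similar composition leaves oat unexcepted although it is the outlier on fibre, available carbohydrate and energy. Rounding explains neither the fibre nor the carbohydrate gap. Confidence in the mismatch is high.

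The consequence is confined to attribution of oat effects on glucose, with carbohydrate the firmer confounder and fibre possibly a minor one. How large the bias is cannot be established from the documents; the figures in step 5 are illustrative. BB versus WWB remains usable for the total-fibre question, and all four breads can still be compared as foods.

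**What to change.** 1. Correct the claim of equality in section 2 and of similarity in section 3.1 so that both agree with Table 1.
2. Base any conclusion of independence from total dietary fibre on BB versus WWB, which differ by 3.1 − 1.4 = 1.7 g β-glucan at 6.9 v 6.8 g total fibre. State the remaining meal differences: carbohydrate +3.5%; protein 12.36 / 13.16 (-6.1%); fat 15.83 / 15.43 (+2.6%); and, if β-glucan is counted in total fibre, other fibre 3.8 v 5.4 g.
3. Report OB versus WWB and OB versus BB as comparisons of breads, naming the carbohydrate and total-fibre differences as confounders.
4. Optionally, show the oat glucose contrasts over assumed carbohydrate elasticities of 0.5 to 1. This would be supportive only, with no pass/fail rule, and labelled post hoc if the data have already been analysed.

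The cost is two corrected sentences, a stated limit on the oat conclusion and one optional calculation from Tables 1 and 2. No new data are needed and the primary model is unchanged. The price is a narrower claim for oat bread.
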